### **5.2.5 Safety Cohort Review**

The study chair, in consultation with the investigator(s), will determine whether the dose will be de-escalated and/or the RP2D dose for the pre-remission therapy phase.

### **5.2.6 Supportive Care and Dose Reduction Guidelines**

#### **5.2.6.1 Infection**

Appropriate broad-spectrum IV antibiotics and/or antifungal agents should be started immediately in patients who develop fever or other signs of systemic infection. In patients with minor infections, venetoclax/DEC-C may be continued in parallel with treatment. Venetoclax dosing should be adjusted to reflect drug interactions.

Treatment with venetoclax and DEC-C should be interrupted in any patient with Grade 4 infection, clinical sepsis (in the absence of documented infection), or neutropenic fever.

After the infection is resolved, venetoclax/DEC-C should be restarted at the previous dose level and per the following guidance:

- In patients prior to achieving remission, venetoclax/DEC-C may be restarted after the patient is clinically recovered (e.g., fever is resolved with no evidence of active infection).
- In patients who have achieved a clinical remission, venetoclax/DEC-C may be restarted after the ANC returns to Grade  $\leq$  2 or baseline, fever has resolved, and patient's condition is stable.

If the neutropenic fever is persistent, or for  $\geq$ 2 occurrences, consultation with the study chair is recommended.

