### 5.2.4 Dose-Limiting Toxicity

A dose-limiting toxicity (DLT) is defined as any toxicity that occurs up to day 28 during the dose de-escalation (pre-remission) phase and is at least possibly related to study drug administration. This does not include toxicity with a clear alternative explanation (e.g., disease progression) or transient ( $\leq 72$  hours) abnormal laboratory values without

associated clinically significant signs or symptoms based on investigator determination. All DLTs will be assessed by the investigator using CTCAE v5.0 criteria.

To be considered evaluable, subjects must fulfill the following minimum criteria:

- All doses of DEC-C.
- 75% of doses of venetoclax during the first cycle (e.g., 21/28 or 16/21 days)

All patients who initiate venetoclax/DEC-C, receive at least one dose of each, and experience a DLT are evaluable regardless of whether the minimum criteria above are met.

Subjects experiencing toxicity that results in dose-holds will remain evaluable provided the minimum criteria outlined above are met. Patients that require dose reductions during the DLT evaluation period (e.g., first 28 days after initiation of the first dose of study treatment/C1D1) will not be considered a DLT so long as they receive the minimum doses at the prescribed dose level outlined above.

Patients who achieve a morphologic remission on C1D22 BMBx, have not experienced a DLT, and have treatment interrupted due to favorable treatment response will be considered evaluable if they complete 75% of protocol-directed doses (i.e., a patient who achieves a remission and is instructed to stop venetoclax on C1D24 is considered evaluable provided they received at least 18/24 venetoclax doses, or 75%) and will not be replaced.

Patients missing >25% of venetoclax doses, or any DEC-C doses due to adverse event(s), will be considered a DLT provided the AEs are considered related. If unrelated, the patient may be replaced as described above.

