**Table 5: Venetoclax/DEC-C Dose Level Summary (Pre-remission Phase)**

DOSE LEVEL	VENETOCLAX	DEC-C
1	400mg once daily Continuous Day 1-28 Δ	100mg/35mg once daily Days 1-5
-1	400mg once daily Continuous Day 1-28 Δ	100mg/35mg once daily Days 1-4
-2	400mg once daily Continuous Day 1-21 Δ	100mg/35mg once daily Days 1-4

\* Cycles are every 28 days.

Δ Venetoclax dosing will be ramped on C1D1 and C1D2 per [Figure 3](#).

During the pre-remission phase, it is intended that venetoclax will be dosed continuously per the dose level summary ([Table 5](#)) and will not be interrupted unless the day C1D22 BMBx is negative for leukemia. Missed days of venetoclax due to treatment interruption in a patient with aplastic marrow that is negative for AML, who are otherwise tolerating therapy well and without evidence of a DLT, will not influence evaluability (i.e., required minimum number of venetoclax doses).

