### 5.2.7 Dose modifications

**Table 7: Toxicity Dose Adjustment Guidelines**

Event	Occurrence	Action
Grade 4 neutropenia with or without fever or infection  OR  Grade 4 thrombocytopenia	Occurrence prior to achieving remission*	
 
Transfuse blood products, administer prophylactic and treatment anti-infectives as clinically indicated.
 
In most instances venetoclax and DEC-C cycles should not be interrupted due to cytopenias prior to achieving remission
 

	First occurrence after achieving remission and lasting ≤ 7 days	
 
Delay subsequent treatment cycle of
 

		
venetoclax and DEC-C and monitor blood counts.
 
 
• Administer G-CSF if clinically indicated (see Section 5.2.6.2)
 
• Once toxicity has resolved to <math>\leq</math> Grade 2, resume venetoclax/ DEC-C at the same dose.
 

	
Subsequent occurrences in cycles after achieving remission and lasting <math>\geq</math> 7 days.
	
 
• Delay subsequent treatment cycle of venetoclax and DEC-C and monitor blood counts.
 
• Administer G-CSF if clinically indicated (see Section 5.2.6.2)
 
• Once toxicity has resolved to <math>\leq</math> Grade 2, resume venetoclax and DEC-C at one dose level lower (see Table 6)
 

\*Consider interim bone marrow biopsy for patients who may have achieved early remission

Table obtained from current venetoclax USPI. Modifications relevant to this study are indicated in underline and bold.

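### For Grade 4 neutropenia with fever before remission, Section 5.2.6.1 and Table 7 give conflicting interruption instructions, and the choice between them can decide whether a missed-dose DLT is counted

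*Combined protocol and SAP*

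**What the plan says.** Four places bear on a patient who has not reached remission and has Grade 4 neutropenia with fever.

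- **Section 5.2.6.1 (Infection).** Both drugs "should be interrupted in any patient with Grade 4 infection, clinical sepsis (in the absence of documented infection), or neutropenic fever". The sentence has no phase limit. The restart conditions that follow include one for the pre-remission phase: "In patients prior to achieving remission, venetoclax/DEC-C may be restarted after the patient is clinically recovered".
- **Section 5.2.7, Table 7.** The event row is "Grade 4 neutropenia with or without fever or infection" (or Grade 4 thrombocytopenia). For occurrences before remission, the cell calls for transfusion and anti-infectives and says that in most instances "cycles should not be interrupted due to cytopenias prior to achieving remission".
- **Section 5.2.6.3, text under Table 5.** The stated intention is that pre-remission venetoclax "will not be interrupted unless the day C1D22 BMBx is negative for leukemia".
- **Section 5.2.4 (Dose-Limiting Toxicity).** A patient who misses more than 25% of venetoclax doses, "or any DEC-C doses due to adverse event(s), will be considered a DLT provided the AEs are considered related". If the event is unrelated, the patient may be replaced. The minimum venetoclax exposure is 75% of cycle 1 doses, given as 21/28 or 16/21.

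**The concern.** The patient described falls under both Section 5.2.6.1 and Table 7. One text tells the site to hold both drugs. The other tells it in most instances to carry on. The text under Table 5 points the same way as Table 7 for venetoclax and makes no exception for infection. No sentence sets precedence and no cross-reference links the three.

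For most supportive-care wording this would be a drafting matter. Here it reaches a decision rule, because a hold creates missed doses and missed doses for a related event are themselves a DLT criterion. Two sites that both follow the protocol could classify the same episode differently. DLT counts decide whether a dose level is accepted (Table 4: 2 or more of 6 moves to the next lower level) and whether enrollment pauses (Table 10: starting at 2 of the first 6). The event is also foreseeable: Section 1.1.4 describes febrile neutropenia as expected and as the most common serious event with venetoclax.

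**Working it through.** **1. Do the instructions overlap?**

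| Text | Covers pre-remission? | Covers fever with Grade 4 neutropenia? | Instruction |
|---|---|---|---|
| 5.2.6.1 | Yes (has its own pre-remission restart condition) | Yes (neutropenic fever, any patient) | Interrupt both drugs |
| Table 7, first row | Yes (occurrence before remission) | Yes (row names fever and infection) | In most instances do not interrupt for cytopenias |
| Text under Table 5 | Yes | Not mentioned, no exception made | Venetoclax intended to continue unless the C1D22 marrow is negative |

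They overlap for Grade 4 neutropenia with fever. Neutropenic fever with a lower grade of neutropenia lies outside the Table 7 row, so for that patient only Section 5.2.6.1 and the text under Table 5 apply.

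**2. When does a hold become a missed-dose DLT?**

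The plan's own threshold reproduces: 0.75 × 28 = 21, and 0.75 × 21 = 15.75, rounded up to 16.

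- 28 venetoclax days: 7 missed is 7/28 = 25.0%, which does not exceed 25%; 8 missed is 8/28 = 28.6%, which does.
- 21 venetoclax days (dose level -2): 5 missed is 5/21 = 23.8%; 6 missed is 6/21 = 28.6%, which crosses.
- DEC-C: one missed dose is enough, so the hold must overlap days 1-5 (days 1-4 at the lower levels).

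A related hold that crosses one of these lines is a DLT. The same episode treated without a hold produces no missed-dose DLT.

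**3. Where does the count go?**

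Table 10 follows from a Beta(1,1) prior: after k DLTs in n patients the posterior is Beta(1+k, 1+n−k), and enrollment pauses when P(p > 0.2) exceeds 0.80. At 2/6 the posterior is Beta(3,5), and P(p > 0.2) = 0.8⁷ + 7(0.2)(0.8⁶) + 21(0.2²)(0.8⁵) = 0.210 + 0.367 + 0.275 = 0.852. The other boundaries also reproduce: 0.839 at 3/10, 0.836 at 4/14, 0.804 at 5/19, 0.811 at 6/23, 0.818 at 7/27, 0.825 at 8/31 and 0.854 at 9/34. The boundaries are sound; the issue is what is counted against them.

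**4. How sensitive are the rules to reclassified events? (assumed rates)**

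The documents give no neutropenic fever rate for this regimen in this population, so the per-patient DLT rates p below are assumptions. With q = 1 − p, Table 4 accepts a level with probability q³ + 3pq² × q³. The Table 10 pause probability is computed exactly, patient by patient from the 6th to the 34th.

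| Assumed DLT rate | Level accepted (Table 4) | Pause by patient 34 (Table 10) |
|---|---|---|
| 10% | 0.729 + 0.177 = 0.906 | 0.154 |
| 20% | 0.512 + 0.197 = 0.709 | 0.570 |
| 30% | 0.343 + 0.151 = 0.494 | 0.898 |

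This shows that the rules respond strongly to a shift in the DLT rate. It does not show that a shift of this size would occur.

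**The case against.** The strongest reply is that a site can obey both texts. Table 7 limits its own reason to cytopenias and is hedged, while Section 5.2.6.1 gives a different reason to hold. Section 5.2.7 lists active or uncontrolled infection separately, under non-hematologic toxicity, and Section 5.2.6.3 expects some pre-remission interruptions because it requires their reasons to be documented. This has force and makes the conflict less than absolute. It does not remove it: the Table 7 row says "with or without fever or infection", its pre-remission cell calls for treatment anti-infectives, and the reader has to supply the precedence.

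The route to a different classification is also narrow. The event must be related, fall in the first 28 days and cause enough missed doses. Before remission, Section 5.2.6.1 allows restart on clinical recovery without waiting for neutrophils. The DEC-C missed-dose text in Section 5.2.1.2 speaks of completing all planned treatment days. A related Grade 3 or 4 infection will generally be a non-hematologic DLT whether or not doses are held. Section 5.2.4 lets the study chair and investigators document that an event is not a DLT, but only in rare instances. Table 10 triggers a pause for review, not closure. These points limit the size of the problem and all stand.

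A reader might make two stronger inferences that the documents do not support:

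- **That febrile neutropenia already puts the DLT rate at or above the 20% limit.** Section 1.2.3 gives 18.2-26.5%, which straddles 20%. It is a serious-event rate from DEC-C studies, not a first-cycle DLT rate for this combination after transplant.
- **That Section 5.2.4 is silent on whether such holds count.** It already counts doses missed for a related adverse event, and the text under Table 5 exempts only interruptions for an aplastic, AML-negative marrow in a patient tolerating therapy without a DLT.

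**Conclusion.** The point holds as a conflict of instructions with a consequence for DLT classification. For Grade 4 neutropenia with fever before remission, one section directs interruption of both drugs, another directs in most instances that cycles continue, and nothing ranks them. Because any DEC-C dose, or 8 or more of 28 venetoclax days, missed for a related event is a DLT, the passage a site follows can change the count that feeds Table 4 and Table 10.

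The size is unknown. It depends on how often the event occurs in cycle 1 with this regimen, how often it is judged related, how long holds last, and how far sites differ; the documents give none of these. The 10%, 20% and 30% figures are illustrations only. The Table 10 boundaries themselves are correct. No view is taken on which clinical instruction is right.

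**What to change.** The sponsor should reconcile Section 5.2.6.1, the text under Table 5 in Section 5.2.6.3, and the pre-remission row of Table 7 for neutropenic fever before remission, and add a cross-reference so that each points to the same rule. The sponsor should then confirm that the reconciled rule is consistent with the missed-dose DLT criterion in Section 5.2.4, which needs no new criterion for this purpose.

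The cost is a short protocol amendment to a few sentences and one table cell. Sample size, dose-level rules and toxicity boundaries do not change.

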#### **5.2.6.2 Colony Stimulating Factors:**

Colony stimulating factors may be used in patients who achieved a CR and have a duration of neutropenia  $\geq$ 35 days, develop neutropenic fever, or significant infectious complication at any time, as deemed warranted to maintain safety of the patient per the investigator.

### 5.2.6.3 Dose Reduction Guidelines

Venetoclax is generally well-tolerated; the most common toxicities observed are fatigue, headache, nausea, diarrhea, hematologic toxicity, and electrolyte abnormalities. Non-hematologic grade 3/4 toxicity is rare. DEC-C is also well-tolerated.

The NCI CTCAE version 5.0 will be used for grading the severity of AEs; the study treatment modifications described below are applied according to this severity grading. Toxicity will be documented as described in [Section 5.2.3](#). If more than one type of toxicity occurs concurrently, the most severe grade will determine the modification. For purpose of any necessary definition, “baseline value” is defined as the most immediately known value in place prior to patient’s first receipt of protocol-indicated treatment on Cycle 1, Day 1.

#### Pre-remission Phase

Treatment interruptions during the pre-remission phase, as well as the reason, must be documented.

Dose reductions are to be avoided for patients during cycle 1 in the dose finding portion of the study. [Figure 1](#) and [Table 5](#) summarizes the starting doses (Dose Level 1) and dose levels. General supportive care guidelines are provided in [Section 5.2.6](#). Outside of the dose finding portion of the study, dose reductions of venetoclax and/or DEC-C for adverse events may take place at any time as otherwise consistent with the protocol.

**Table 5: Venetoclax/DEC-C Dose Level Summary (Pre-remission Phase)**

DOSE LEVEL	VENETOCLAX	DEC-C
1	400mg once daily Continuous Day 1-28 Δ	100mg/35mg once daily Days 1-5
-1	400mg once daily Continuous Day 1-28 Δ	100mg/35mg once daily Days 1-4
-2	400mg once daily Continuous Day 1-21 Δ	100mg/35mg once daily Days 1-4

\* Cycles are every 28 days.

Δ Venetoclax dosing will be ramped on C1D1 and C1D2 per [Figure 3](#).

During the pre-remission phase, it is intended that venetoclax will be dosed continuously per the dose level summary ([Table 5](#)) and will not be interrupted unless the day C1D22 BMBx is negative for leukemia. Missed days of venetoclax due to treatment interruption in a patient with aplastic marrow that is negative for AML, who are otherwise tolerating therapy well and without evidence of a DLT, will not influence evaluability (i.e., required minimum number of venetoclax doses).

#### Initiating Post-remission Phase (Cycle 1)

Patients will begin the post-remission phase of the study after achieving blast clearance from their marrow. Patients with marrow aplasia must recover peripheral blood counts with ANC of  $\geq 1000/\text{mm}^3$  /  $1 \times 10^9/\text{L}$ . Patients with cellular marrows may proceed to the post-remission phase of the study without count recovery if the treating physician believes the cellularity is disease related. Discussion with the study chair is recommended.

Patients with marrow aplasia on C1D22 or C2D22 BMBx will have venetoclax interrupted until the absolute neutrophil count (ANC) recovers to  $\geq 1000/\text{mm}^3$  /  $1 \times 10^9/\text{L}$ . If persistent grade 4 cytopenias, repeat BMBx will be performed at D42. If persistent marrow aplasia without disease, patients will be managed expectantly until  $\geq 1000/\text{mm}^3$  /  $1 \times 10^9/\text{L}$ . A BMBx will be repeated every 6 weeks until ANC recovery. At that time, patients will enter the post-remission phase (See [Figure 2](#)).

To proceed with each cycle of post-remission therapy, platelets/ANC must be improved to grade 2 or higher:

Platelets  $\geq 50,000/\text{mm}^3$  /  $50.0 \times 10^9/\text{L}$   
Neutrophils  $\geq 1000/\text{mm}^3$  /  $1 \times 10^9/\text{L}$

Venetoclax and DEC-C are generally intended to be dosed in combination but may be separably dosed for up to 28 consecutive days. The dose levels of venetoclax and DEC-C are indicated in [Table 5](#).

In the event of an adverse event deemed by the study physician as unrelated to protocol-indicated treatment, the study physician may choose to precautionarily interrupt venetoclax and/or DEC-C for up to 28 days, but no dose reduction of either agent should occur.

Venetoclax and/or DEC-C may be delayed for any adverse event, laboratory abnormality, or intercurrent illness which, in the judgment of the investigator, warrants delaying the dose of DEC-C and/or venetoclax. If either or both drugs are interrupted for  $>4$  weeks for reason other than treatment-related cytopenias, discussion with the study chair is recommended.

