### **Subsequent Post-remission Therapy (Cycle 2+)**

Patients without clinical or laboratory evidence of relapse will continue to receive therapy with DEC-C/venetoclax for maintenance of response (See [Figure 1](#) and [2](#)). Subsequent post-remission cycles will be initiated after evidence of count recovery, defined as:

Platelets  $\geq 50,000/\text{mm}^3$  /  $50.0 \times 10^9/\text{L}$   
Neutrophils  $\geq 1000/\text{mm}^3$  /  $1 \times 10^9/\text{L}$

In patients who recover counts within 6 weeks of CxD1, and are otherwise tolerating therapy, subsequent post-remission cycles will occur at the same dose level.

If count recovery is delayed >6 weeks beyond CxD1, patients will be reduced by one dose level (e.g., a patient with count recovery lasting 7 weeks after post-remission C1 will dose C2 at dose level -1).

For patients with delayed count recovery (>6 weeks) at dose level -3, discussion with the study chair is recommended.

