**Table 6: Venetoclax/DEC-C Dose Level Summary (Post-remission Phase)**

DOSE LEVEL	VENETOCLAX	DEC-C
1	400mg/day dosed continuously	100mg/35mg Days 1-5
-1	400mg/day 21/28 days	100mg/35mg Days 1-4
-2	400mg/day 14/28 days	100mg/35mg Days 1-3
-3	400mg/day 7/28 days	100mg/35mg Days 1, 3, and 5

\* Cycles are every 28 days.

Patients who are experiencing low-grade tolerability symptoms and are deriving clinical benefit from the treatment may have their dose reduced, or subsequent cycle delayed, at the discretion of the PI. Dose reductions should be done in accordance with [Table 6](#). Patients whose dose or schedule is reduced may subsequently be re-escalated to the previous dose upon improvement of the tolerability, at the discretion of the PI. PI may consult with the study chair as necessary.

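### Post-remission Cycle 1 is sent to the pre-remission dose table, so a patient who enters that phase at level -1 or -2 has conflicting regimens under one label and no stated mapping between the two scales

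*Combined protocol and SAP*

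**What the plan says.** In Section 5.2.6.3, the subsection on starting post-remission therapy (Cycle 1) states: "The dose levels of venetoclax and DEC-C are indicated in" Table 5. That table is captioned "Venetoclax/DEC-C Dose Level Summary (Pre-remission Phase". Table 6, which follows the subsection on Cycle 2 and later, is captioned "Venetoclax/DEC-C Dose Level Summary (Post-remission Phase". The two tables share the labels 1, -1 and -2; level -3 exists only in Table 6.

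For later post-remission cycles, a patient whose counts recover within six weeks stays at the same level. If recovery takes longer, "patients will be reduced by one dose level". The worked example there moves a patient to level -1 for Cycle 2, and the next paragraph refers to level -3.

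Three other places tie post-remission reductions to Table 6: the note under Table 6, the last row of Table 7 (Section 5.2.7), and the additional considerations on hematologic toxicity that follow Table 7.

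In Sections 7.3 to 7.8, the dosing line of each pre-remission and post-remission visit cites Tables 5 and 6 together.

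**The concern.** A site that follows the text literally takes the Cycle 1 post-remission regimen from a table captioned for another phase, then applies reductions from a second table in which the same labels stand for different schedules. The visit lists do not resolve this, because they name both tables everywhere.

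Reduced entry is a planned branch. Table 4 de-escalates the recommended phase 2 dose (RP2D) after two or more DLTs at a level, and the sample-size text budgets 6 to 12 extra patients for a toxic starting level. Outside the dose-finding portion, Section 5.2.6.3 also allows individual pre-remission reductions for adverse events, which Section 5.2.7 narrows to non-hematologic ones.

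If the branch is used in this multi-center trial, patients recorded at one level could receive different exposure. That bears on cytopenias and count recovery, on relapse-free survival (a secondary objective), and on the planned correlation of immune subsets with dosing schedule (Sections 8.1 and 8.2.2).

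**Working it through.** The plan gives no figure to reproduce. The check compares the tables cell by cell and then follows the rules for each entry level.

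**Step 1. Scheduled days per 28-day cycle (venetoclax / DEC-C).** Venetoclax is 400 mg on each dosing day in both tables; the Cycle 1 ramp is ignored.

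| Level | Table 5 | Table 6 | Table 6 relative to Table 5 |
|---|---|---|---|
| 1 | 28 / 5 | 28 / 5 | identical |
| -1 | 28 / 4 | 21 / 4 | venetoclax 1 − 21/28 = 25% fewer days; DEC-C equal |
| -2 | 21 / 4 | 14 / 3 | venetoclax 1 − 14/21 = 33% fewer days; DEC-C 1 − 3/4 = 25% fewer days |
| -3 | none | 7 / 3 | only in Table 6 |

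At level -1, for example, Table 5 reads "400mg once daily Continuous Day 1-28" and Table 6 reads "400mg/day 21/28 days". In venetoclax per cycle, level -1 is 28 × 400 = 11,200 mg against 21 × 400 = 8,400 mg, and level -2 is 8,400 mg against 14 × 400 = 5,600 mg.

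**Step 2. Do the scales map onto each other?** Table 5 level -1 (28 / 4) matches no row of Table 6. Table 5 level -2 (21 / 4) is the same regimen as Table 6 level -1. The labels are therefore not interchangeable, and one Table 5 regimen has no Table 6 label.

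**Step 3. Entry at level 1.** Both tables give 28 / 5 in Cycle 1. A one-level reduction goes to Table 6 level -1 (21 / 4). There is no conflict.

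**Step 4. Entry at Table 5 level -1, Cycle 1 taken from Table 5 (28 / 4).**
- Timely recovery, same level: by regimen the patient stays at 28 / 4, which Table 6 does not list. By label, read in Table 6, the patient moves to 21 / 4, a 25% drop in venetoclax days that no toxicity triggered.
- Delayed recovery, one level lower: by regimen, the next lower Table 6 row is 21 / 4. By label, the patient goes to Table 6 level -2, 14 / 3.

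**Step 5. Entry at Table 5 level -2, Cycle 1 taken from Table 5 (21 / 4).**
- Timely recovery: by regimen 21 / 4; by label in Table 6, 14 / 3.
- Delayed recovery: by regimen the patient is at Table 6 level -1 and moves to level -2, 14 / 3. By label the patient moves to level -3, 7 / 3.

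In Steps 4 and 5 each rule gives two different regimens, and no readable sentence chooses between them.

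**The case against.** A reader might infer that a one-level reduction has no single meaning anywhere in the post-remission phase. The documents do not support that. The note under Table 6, Table 7 and the considerations after it all direct post-remission reductions to Table 6, and the Cycle 2+ text mentions level -3, which only Table 6 contains. For a patient who starts at level 1, one level down is Table 6 level -1.

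A reader might also take the 25% to 33% differences as exposure gaps to be expected between sites. They are not. They compare two tables captioned for different phases, and different scales by phase appear deliberate: Section 5.2.2 is restricted to the pre-remission phase, and Section 5.2.5 sets the RP2D for that phase only. If all dosing starts at level 1, the Table 5 reference changes nothing.

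The reference could also be intended, with the pre-remission level carried into post-remission Cycle 1 and Table 6 used for reductions thereafter. The DEC-C row of the schedules (Tables 2 and 3), labelled RP2D across the post-remission columns, is compatible with this. No readable text says so, however, and even on this reading the entry point into Table 6 is undefined for a patient at Table 5 level -1 or -2. Figure 2, to which the subsection refers, may contain the missing rule; its graphic was not available.

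The limits to level 1 and to post-remission reductions stand. They narrow the point but do not remove it.

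**Conclusion.** The plan is wrong as written; this is an internal inconsistency and not a design choice. The post-remission Cycle 1 text cites a table captioned for the other phase, the Section 7 dosing lines cite both tables throughout, and the staying and stepping-down rules are undefined in the readable text for patients who enter at a reduced level.

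The size is conditional on such entry, through an RP2D of -1 or -2 or an individual pre-remission reduction for non-hematologic toxicity. It is then 7 venetoclax days per cycle at either label (28 against 21, or 21 against 14), plus one DEC-C day at level -2. For entry at level 1 it is zero.

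The table comparison and the cross-references are certain. The absence of a mapping rule is less so, because Figures 1 and 2 could not be seen. No effect is claimed on the two-stage efficacy rule, and any effect on the DLT rules should be limited, since the 28-day DLT window precedes most post-remission dosing.

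**What to change.** The sponsor should reconcile Section 5.2.6.3, Tables 5 to 7, the considerations after Table 7, and the dosing lines in Sections 7.3 to 7.8:

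1. Name the one table that governs post-remission Cycle 1.
2. State how a patient at pre-remission level -1 or -2 enters the Table 6 scale, and what the same level and one level lower mean for that patient. If Figure 2 already gives this rule, repeat it in the text.
3. Make each dosing line in Section 7 cite only the table for its phase.
4. Preferably give the two scales distinct labels, so that a recorded level identifies one regimen in the analysis data.

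Which regimen applies is for the sponsor to decide. The cost is a protocol amendment to wording, labels and cross-references, with no change to sample size or analysis.
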